2.2.2 Sexuality

Main objectives:

- 1. To assess the incidence of hematospermia in PWH.
- 2. To describe the presence of limitations in sexual health due to haemophilia in PWH.

2.3 General objective: To assess quality of care of PWH

2.3.1 General quality of care

Main objective:

- 1. To assess quality of care from a patient's perspective, including information provision, communication with care providers and financial consequences of health care services use.
- 2. To assess treatment satisfaction of PWH.

2.3.2 Transition

Main objectives:

- 1. To compare adherence in adolescents and young adults with severe haemophilia with adherence in other age groups
- 2. To assess the relationship between self-efficacy, treatment adherence and self-reported readiness for transition in adolescents and young adults with severe haemophilia.

Secondary objective:

1. To assess the relationship between adherence, factor use, absence from work or school and bleeding outcomes in young adults with severe haemophilia.

2.3.3 Desmopressin use

Main objectives:

1. To assess desmopressin use, perceived side effects, barriers for use and information provision by clinicians in patients with mild and moderate haemophilia A.

2.3.4 Patient views on new haemophilia treatment options

Main objective:

1. To assess patients' perceptions of new treatment options (including gene therapy, extended halflife clotting factors, non-replacement coagulation factor therapies and tailored prophylaxis by using pharmacokinetic dosing)

2.3.5 Needle fear

Main objective:

1. To assess the prevalence of needle fear or needle phobia among PWH.

Secondary objective:

1. To assess the association between needle fear and adherence.

2.4 General objective: To elucidate the variability in clinical phenotype among PWH

2.4.1 To assess the usefulness of The Calibrated Automated Thrombogram (CAT) assay in relation to clinical phenotype:

Main objectives:

1. To establish specific sample conditions to generate reliable CAT assay outcome parameters in patients with haemophilia.

Secondary objectives:

- To assess the association between the results of the CAT assay and the self-reported clinical bleeding phenotype of patients with severe, moderate and mild haemophilia.
- 2. To evaluate if the CAT assay can accurately diagnose the self-reported clinical bleeding phenotype of patients with severe, moderate and mild haemophilia.

2.4.2 To assess the usefulness of the Nijmegen Haemostasis Assay (NHA) in relation to clinical phenotype:

Main objectives:

- To assess the association between the results of the NHA and the self-reported clinical bleeding phenotype of patients with severe, moderate and mild haemophilia A and B.
- To evaluate if the NHA can accurately diagnose the self-reported clinical bleeding phenotype of patients with severe, moderate and mild haemophilia.

2.4.3 To assess misclassification of disease severity by the one-stage clotting assay in haemophilia B patients:

Main objectives:

 To assess the extent of discrepancy in FIX activity level as measured by the one stage clotting assay to the chromogenic assay in patients with mild and moderate haemophilia B. 2. To evaluate the association between F9 genotype and discrepancy between the FIX activity levels as measured by the one-stage clotting assay and the chromogenic assay in patients with mild and moderate haemophilia B.

2.4.4 To describe bleeding scores in children with haemophilia with the newly developed paediatric bleeding assessment tool (iCHEC):

Main objective:

- 1. To describe bleeding scores in all children with haemophilia
- 2. To describe bleeding scores according to haemophilia severity, age and treatment regimen (prophylaxis/on demand).

2.5 General objective: To assess immunological mechanisms that may lead to inhibitor formation in patients with haemophilia A

2.5.1 Specific objectives assessing the relationship between FVIII-specific non-neutralizing antibodies and inhibitor formation:

Primary objectives:

- 1. To assess the prevalence of FVIII-specific non-neutralizing antibodies (NNAs) among noninhibitor patients with severe, moderate and mild haemophilia A in the Netherlands.
- To characterize all FVIII-specific antibodies with respect to Ig class, IgG subclass and affinity, and to evaluate whether some of these characteristics are more associated with having neutralizing antibodies (inhibitors) rather than non-neutralizing antibodies (NNAs).

Secondary objectives:

- 1. To assess whether F8 genotype and polymorphisms in immune response genes influence the development of non-neutralizing antibodies (NNAs).
- To assess whether F8 genotype and polymorphisms in immune response genes influence the development of either neutralizing antibodies (inhibitors) or non-neutralizing antibodies (NNAs).
- 3. To evaluate the association between non-neutralizing antibodies (NNAs) and bleeding frequency in patients with severe haemophilia A.
- 4. To evaluate potential misclassification of low-titre inhibitors as non-neutralizing antibodies

in patients with haemophilia A.

5. To evaluate the diagnostic performance of a modified FVIII ELISA for detection of FVIIIspecific antibodies (inhibitors), using the Bethesda assay as the reference test.

2.5.2 Specific objectives assessing dendritic cell response and T-cell activation in the FVIII immune response:

Primary objectives:

[figure not shown]
- To compare the expression of interleukin-2 and TGF-beta in monocyte-derived dendritic cells after stimulation with FVIII with and without danger signals (e.g. LPS) in patients with nonneutralizing FVIII-specific antibodies (NNAs) and patients without any current FVIII-specific non-neutralizing antibodies.
- To compare the regulatory T- cell count, as a proportion of all CD4+ T-cells in patients with non-neutralizing FVIII-specific antibodies (NNAs) or patients without any current FVIIIspecific antibodies.

Chapter 3 - Study design

HiN-6 study design

The HiN-6 study will consist of both cross-sectional and longitudinal observational studies, according to the specific research objective. A mixed-methods approach will be used for data collection and analysis. All participants will be asked to fill out a questionnaire and to provide a blood and urine sample. In addition, information will be obtained from medical records. For some of the planned substudies, a smaller number of patients will be asked to provide an additional blood sample at a second visit. Detailed study procedures can be found in chapter 5.

The HiN-6 is the sixth iteration of a series of cross-sectional studies. By combining information from previous HiN studies with the current HiN-6 study, we will also be able to perform a number of longitudinal analyses (see Chapter 6 for specific substudies).

Chapter 4 - Study population

4.1 Population

All male Dutch patients with severe, moderate, or mild haemophilia A or B who are registered as such at one of the seven haemophilia treatment centres in the Netherlands will be eligible for inclusion. In addition, currently deceased patients that participated in the HiN-5 questionnaire in 2001 will also be eligible for inclusion. Severe haemophilia A or B is defined as having FVIII or FIX levels <0.01 IU/ml, moderate haemophilia A or B is defined as having FVIII or FIX levels between 0.01-0.05 IU/ml and mild haemophilia A or B is defined as having FVIII or FIX levels >0.05-0.40 IU/ml.

4.2 Inclusion criteria

- Male patients with severe, moderate or mild congenital haemophilia A or B with endogenous clotting factor activity levels <0.40 IU/ml who are registered at one the haemophilia treatment centres in the Netherlands.
- Male patients with congenital haemophilia A or B who underwent liver transplantation in the past (irrespective of their endogenous clotting factor levels).
- All currently deceased male haemophilia A or B patients that participated in the HiN-5 questionnaire in 2001.
- For patients \geq 16 years old; written informed consent.
- For patients 12-15 years old; written informed consent from both the patient and their parents/legal guardian(s).
- For patients <12 years old; written informed consent from their parents/legal guardian(s).

4.3 Exclusion criteria

Patients with the following criteria will be excluded from the study:

- Female carriers of haemophilia A or B
- Patients with acquired haemophilia.
- Non-haemophilic patients with reduced FVIII levels due to VWD.

4.4 Sample size calculation

We aim to include the entire Dutch haemophilia population (roughly 1800 patients). Based on the response rate of the 5 previous HiN studies, we expect a response rate of around 70%, which corresponds to 1260 patients.

Chapter 5 - Methods

5.1 Data collection

Data will be collected through questionnaires filled in by each participant (see 5.1.1), blood/urine samples obtained from each participant (see 5.1.2) and from each participant's medical record using case report forms (see 5.1.3).

5.1.1 Questionnaires

Patients will receive a letter from their physician with a personal log in code to an electronic questionnaire. They will be reminded after one month to fill out the questionnaire online. Patients who are unwilling or unable to fill out the questionnaire electronically will be provided with a hard copy of the questionnaire. The following subjects are included in the questionnaire:

- demographic characteristics
- socio-economic characteristics
- clinical characteristics (bleeds, treatment, inhibitors, other medication), HIV status (patients born before 1985) and hepatitis C status (patients born before 1992).
- medical history: other chronic conditions, hospital admissions, colon cancer screening
- sexuality
- general health status / quality of life (RAND-36, PROMIS29)[77, 78]
- sports, physical activity and self-reported physical performance (MAQ, HEP-TEST-Q)[79, 80]
- functional limitations (HAL)[81]
- adherence (VERITAS-pro)[82, 83]
- pain
- needle fear
- self-management (PAM-13)[84]
- fear of falling (FES)
- experience with care, novel treatment options
- treatment satisfaction (Hemo-SAT)[85]

Children's versions of the questionnaire will be available for children up to 17 years old. In general,

children from 12-17 years old will fill out the questionnaire independently. For children under 12 years old, parents will fill out most of the questions. Topics covered in the children's questionnaire are listed below:

- socio-demographic characteristics
- daily life
- clinical characteristics (bleeds, treatment, inhibitors)
- medical history (hospital admissions, medications used)
- pain
- needle fear
- sports and physical activity (MAQ, HEP-test-Q)[79, 80]
- quality of life (CHO-KLAT [86])
- functional limitations (PedHAL [88])
- self-efficacy (HSES)[89]
- bleeding score (iCHEC)
- treatment satisfaction (Hemo-SAT)[85]

Adolescents (15-25 years) will either fill out the children's version of the questionnaire if they are younger than 18 years old, or the adult version if they are 18 or over. In addition, individuals in the 15-25 age group will fill out a self-efficacy questionnaire (HSES) [89] Patients older than 65 years will be asked to fill out the modified Falls Efficacy Scale (FES)[90]. An overview of used questionnaires is provided in Appendix 3.

In total, the questionnaire will take approximately 40-120 minutes to complete, depending on which questions are relevant to the patient (e.g. patients born after 1992 will not fill out questions about hepatitis C and HIV infections). The electronic questionnaire system will automatically skip questions if they are not relevant for that particular patient.

The questionnaire will be built into the Castor software.

5.1.2 Blood and urine sampling

First visit (all participants):

All participants will be asked to provide a blood/urine sample during a regular visit to the

haemophilia treatment centre. Part of the blood sample will be used for this study, the remainder of the blood sample and the entire urine sample will be stored in a national biobank for future research purposes. (see table 1) The biobank will be part of the "Parelsnoer Institute", a national organization that provides the infrastructure for the establishment of clinical biobanks in all Dutch university medical centres. Additional information about the biobank and the Parelsnoer Institute is provided in the following documents:

- Parelreglement Parel Hemofilie (version 5.1)
- Parelsnoer Kaderreglement (version 3.1)

Blood is sampled at least 3 days after the last FVIII or DDAVP administration, at least 5 days after the last FIX administration and at least 7 days after resolution of a bleed. Blood sampling is voluntary. Depending on the age of the patient, 7.2 to 55 ml of blood will be drawn through venepuncture. Sampling of 1-5% of an individual's total blood volume is deemed safe according to WHO guidelines. [91] In the current project the maximum sampling volume will be set at 2.5% of the total blood volume. At the first visit, between 7.2-55 ml (depending on the age of the patient) of blood will be collected from all participants. (see table 1)

In addition, 10 ml of midstream urine will be collected from all adults and toilet-trained children. To minimize patient inconvenience, a spot urine sample will be collected instead of a 24-h urine sample. (see table 1)

Age category	Total drawn blood volume	Citrated plasma for HiN- 6 study	Serum and/or citrated plasma for biobank	DNA sample for HiN-6 study/biobank	Urine sample for biobank*
0-4 years	7.2 ml	2.25 ml plasma	1.35 ml plasma	Obtained from	10 ml
4-10 years	9ml	2.25 ml plasma	2.25 ml plasma	citrate tubes	10 ml midstream
10-12 years	17,5ml	2.25 ml plasma	2 ml serum, 4.5 ml plasma	after removal	urine
>12 years	55 ml	6.75 ml plasma	5 ml serum, 15.75 ml plasma	of plasma	

Table 1: blood, urine and DNA collection during the first visit

*: Children that are not toilet trained are excluded.

Blood samples will be used for the following experiments:

• The Nijmegen Haemostasis Assay (NHA). [60]

- The Calibrated Automated Thrombogram (CAT) assay. [59]
- Bethesda assay: We will measure the presence of inhibitors using the Bethesda assay with Nijmegen modification. A titre of at least 0.6 Bethesda Units is required to be positive for this assay. The cut-off point for low-titre vs high-titre inhibitors is 5.0 Bethesda Units. [92]
- Low-titre inhibitor assay: To assess the presence of low-titre inhibitors, we will use a lowtitre inhibitor assay. ([name], personal communication)
- ELISA: We will assess the presence and characteristics of FVIII-specific antibodies in our full cohort using a highly sensitive and fully validated ELISA platform developed by Whelan et al.
 [70] In patients who are positive for antibodies using this assay we will characterize the isotype (IgA, IgM and IgG) and for the IgG isotype also the subclass (IgG1 to 4). Samples with confirmed specificity for FVIII will also be assessed for apparent affinity.

The apparent affinities of FVIII-specific antibodies for all immunoglobulin isotypes and IgG subclasses will be assessed using a competition-based ELISA approach by Hofbauer et al. The affinity assessment is based on the availability of antibody for binding to FVIII-coated ELISA plates after competition with FVIII in solution. [71]

• Other laboratory tests such as:

- FVIII and FIX activity using one-stage assay
- FVIII and FIX activity using chromogenic assay
- FVIII and FIX antigen level
- FVIII genotype (if unknown)
- FVIII haplotype
- HLA/IL-10/TNFα/CTLA4/HO-1/FcgR gene variants

Second visit (50 adult participants):

Based on the results of the first analyses, we will draw an additional 50 mL of blood in 50 selected participants during a second visit to the haemophilia treatment centre. This second sample will be only be used for this substudy and will not be stored in the biobank. Blood samples will be used for the following experiments: • **Regulatory T cell count:** Regulatory T cell count will be assessed using both flow cytometry and a quantitative real-time PCR assay developed by Epiontis (Epiontis Treg assay).

Flow cytometry

After stimulation of PBMCs with FVIII, we will quantify all T-cell subsets using flow cytometry. PBMCs will be stained with monoclonal antibodies against cell receptors specific for a certain T-cell subset (e.g. CD4+, CD25high, CD127low, FOXP3+ for T-regulatory cells) [93] and markers of T-cell activation (e.g. CD154) [94].

Epiontis Treg assay

DNA will be isolated from whole blood using the DNeasy blood and tissue kit (QIAGEN) according to the manufacturer's protocol. We will use a quantitative real-time PCR assay developed by Epiontis (Epiontis Treg assay). This assay measures the number of FOXP3 genomic DNA copies lacking covalent modifications at CpG sites in the Treg-specific demethylated region. Demethylation of the FOXP3 gene is a highly specific epigenetic marker for T-regulatory cells. [95]

• Dendritic cell response to FVIII:

Isolation

Peripheral blood mononuclear cells (PBMCs) will be isolated from buffy coats by density gradient centrifugation with Ficoll. Monocytes will be purified from PBMCs by positive selection using CD14 MicroBeads. To generate monocyte-derived dendritic cells (moDCs), CD14+ monocytes will be cultured in 96-well tissue culture plates in the presence of GM-CSF and IL-4 for five days at 37 °C, 5 % CO2. [96]

Stimulation of moDCs and analysis

MoDCs will be stimulated with FVIII in combination with and without additional substances that are expected to act as activating 'danger signals' (such as IFN γ , TNF α , and TLR ligands of both microbial and endogenous origin) or 'tolerogenic signals' (such as IL10). The cytokine response will be analysed using Luminex (BioRAD) and the transcriptome using RNA-seq (AMC Amsterdam).

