1.3.4 Patient views on new treatment options

It is important to understand patient preferences and expectations for novel therapeutic options, such as pharmacokinetic-guided clotting factor dosing, gene therapy, FVIII/FIX products with extended half-lives and bi-specific antibodies. This information can be used to better inform patients about treatment innovations thereby increasing the chance of successful implementation.

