1.4.2 The Nijmegen Haemostasis Assay (NHA)

Although thrombin generation reflects the patients' coagulation status, it does not entirely represent the in vivo situation of the patient because it does not take fibrinolysis into account. The NHA uses two fluorescent substrates with non-interfering fluorescent excitation and emission spectra to measure both thrombin and plasmin generation in a single well by a fluorimeter. [60] The assay has been shown to be sensitive for severe haemophilia A, reflected by severely diminished thrombin generation and, due to lack of TAFI activation, increased plasmin generation. Moreover, the assay is also sensitive for FV Leiden, the poly A prothrombin mutation and variations in Protein C and S activity. [60, 61]

1.4.3 Misclassification of disease severity by the one-stage clotting assay in haemophilia B patients

FVIII and FIX activity is most often assessed using the one-stage clotting assay. [62] Several studies have observed a discrepancy in factor VIII activity between the one-stage clotting assay and the chromogenic assay in patients with mild and moderate haemophilia A. More specifically, a higher factor VIII activity was found with the one-stage assay, compared to the chromogenic assay. [63-67] Several studies have found that certain FVIII mutations are associated with this discrepancy. [64, 67, 68]

Misclassification of disease severity by the use of the one-stage clotting assay could have important ramifications; patients could be designated as having a milder bleeding risk, potentially leading to undertreatment of patients. All almost studies have focused on haemophilia A, with the exception of one recent conference paper [69] which also found a discrepancy between the one-stage clotting

assay and the chromogenic assay.

Given the scarcity of evidence for this phenomenon in the haemophilia B population, the HIN-6 study will assess the extent of misclassification of disease severity by re-evaluating the baseline FIX activity using the chromogenic FIX assay in all haemophilia B patients.

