Determinants: The following parameters of the CAT assay will be used as determinants; lag-time, time to peak, peak height and endogenous thrombin potential. FVIII concentration (measured using the chromogenic assay) will also be used as a determinant.

Endpoint: The modified bleeding severity score developed by Schulman et al [97] will be applied to this study population (see paragraph 5.1.3) and used as a dichotomous outcome. Mild bleeders will be defined as being in the lowest two quartiles of the modified bleeding severity score, severe bleeders will be defined as being in the highest two quartiles of the modified bleeding severity score. **Statistical analysis:** The CAT assay parameters and FVIII concentration will be used to predict if a patient is a mild or a severe bleeder (based on the modified bleeding severity score). We will quantify diagnostic performance by constructing ROC-curves for each parameter of the CAT assay

and for FVIII concentration. We will then test if the AUROC of each parameter of the CAT assay differs significantly from the AUROC of the chromogenic assay. This analysis will be performed for the total population and separately for each category of severity.

6.4.2 To assess the usefulness of the Nijmegen Haemostasis Assay (NHA) in relation to clinical phenotype:

Primary objective 1: To assess the association between the results of the NHA and the self-reported clinical bleeding phenotype of patients with severe, moderate and mild haemophilia A and B.
Study design and population: A cross-sectional study design will be used. The population will consist of all haemophilia A and B patients in the Netherlands.

Determinant: The following parameters of the NHA will be used as determinants; lag-time, thrombin peak-time, thrombin peak-height, area under the curve (AUC), fibrin lysis time (FLT), plasmin peak-height and plasmin potential.

Potential confounders: FVIII/FIX genotype, VWF antigen levels and VWF activity.

Endpoint: The modified bleeding severity score developed by Schulman et al [97] will be used as the endpoint (see paragraph 5.1.3). **Statistical analysis:** The association between each parameter of the NHA and bleeding severity will be assessed using linear regression.

Primary objective 2: To evaluate if the NHA can accurately diagnose the self-reported clinical bleeding phenotype of patients with severe, moderate and mild haemophilia.

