Study design and population: A cross-sectional study design will be used. The population will consist of all haemophilia A and B patients in the Netherlands.

Determinants: The following parameters of the NHA will be used as determinants; lag-time, thrombin peak-time, thrombin peak-height, area under the curve (AUC), fibrin lysis time (FLT), plasmin peak-height and plasmin potential. FVIII concentration (measured using the chromogenic assay) will also be used as a determinant.

Other potential predictors of clinical bleeding phenotype: FVIII/FIX genotype, VWF antigen levels and VWF activity.

Endpoint: The modified bleeding severity score developed by Schulman et al [97] will be applied to this study population (see paragraph 5.1.3) and used as a dichotomous outcome. Mild bleeders will be defined as being in the lowest two quartiles of the modified bleeding severity score, severe bleeders will be defined as being in the highest two quartiles of the modified bleeding severity score. **Statistical analysis:** Firstly, we will perform univariate logistic regression using FVIII concentration as

the determinant (the basic prediction model). To quantify the incremental value of the NHA parameters, they will be added to the basic prediction model to create the full prediction model. For internal validation, bootstrapping techniques will be used to reduce overfitting. Agreement between observed and predicted outcomes will be assessed using a calibration plot. Discrimination will be assessed by calculating the AUROC of the full model. The added value of the NHA will be assessed by comparing the AUROC of the basic model (only FVIII concentration) with the AUROC of the full model (FVIII concentration + NHA parameters).

6.4.3 To assess misclassification of disease severity by the one-stage clotting assay in haemophilia B patients:

Primary objective 1: To assess the extent of discrepancy in FIX activity level as measured by the one stage clotting assay to the chromogenic assay in patients with mild and moderate haemophilia B.
Study design and population: A cross-sectional study design will be used. The population will consist of all persons with mild and moderate haemophilia B.

Determinant: FVIII activity level, as determined by the chromogenic assay.

Endpoint: FVIII activity level, as defined using the one-stage clotting assay.

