The risk of bleeding associated with a FVIII wash-out phase of three days for haemophilia A patients and a FIX wash-out phase of five days for haemophilia B patients is minimal. All studies that aim to measure baseline FVIII/FIX levels require such a washout phase, there is no mention of a significantly increased risk of bleeding in the literature as a result of this washout phase. Given the half-life of FVIII and FIX, the increase in bleeding risk is predicted to be minimal.

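### The single 5-day FIX interval in 5.1.2, which 7.4 treats as the wash-out for baseline levels, is not a wash-out for extended half-life FIX products

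*Protocol*

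**What the plan says.** Section 5.1.2 (first visit) gives the rule: "Blood is sampled at least 3 days after the last FVIII or DDAVP administration, at least 5 days after the last FIX administration". The same sentence also requires a week from the end of any bleed. Section 7.4 calls the three and five days the FVIII and FIX wash-out phases and states their purpose: "All studies that aim to measure baseline FVIII/FIX levels require such a washout phase".

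The protocol knows that products differ. Section 1.3.4 mentions "FVIII/FIX products with extended half-lives". Section 4.3 opens with "Patients with the following criteria will be excluded from the study" and lists female carriers, acquired haemophilia and low FVIII due to von Willebrand disease; none of these concerns the product used. The case report form (Appendix 1, item 2.3.1) lists Alprolix and Idelvion among current FIX products and offers prophylaxis frequencies per 1 week and per 2 weeks.

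The sample has several uses:
- Section 1.4.3 plans "re-evaluating the baseline FIX activity using the chromogenic FIX assay in all haemophilia B patients".
- The NHA objectives in 6.4.2 cover "all haemophilia A and B patients in the Netherlands".
- The CAT objectives in 6.4.1 use 25 severe, 25 moderate and 25 mild patients.
- Section 6.4.3 covers "all persons with mild and moderate haemophilia B" and counts a chromogenic/one-stage ratio under 0.6 as a large discrepancy.

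Section 5.1.3 and Appendix 2 record the product, dose and time of the last infusion; Appendix 2 adds body weight.

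**The concern.** A wash-out is long or short only in relation to the half-life of what is being washed out. Five days may suffice for a standard FIX concentrate and be far too short for one designed to last a week or more. The protocol fixes one figure for both and describes it as giving baseline levels.

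If infused factor is still present, FIX activity is overstated, and the NHA and CAT curves describe a treated rather than an untreated patient. In 6.4.2 the bleeding score used as the outcome has factor consumption as one of its two components (5.1.3), so treatment would enter both sides of the association. In 6.4.3, residual factor that both assays read alike pulls the ratio towards 1 and can hide a real discrepancy.

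**Working it through.** **Inputs from the protocol.** Minimum interval 120 h for FIX and 72 h for FVIII; 168 h after the end of a bleed (5.1.2). Severity limits in 4.1: severe below 0.01 IU/ml, and "moderate haemophilia A or B is defined as having FVIII or FIX levels between 0.01-0.05 IU/ml". Ratio cut-off 0.6 (6.4.3; its endpoint text uses FVIII symbols, read here as FIX because the objective concerns FIX).

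**Assumptions, none from the protocol.** Half-life: extended FIX 50-100 h, standard FIX 18-24 h, extended FVIII 15-19 h, standard FVIII 8-14 h. Dose 25-50 IU/kg. Recovery 0.008-0.013 IU/ml per IU/kg for FIX and 0.02 for FVIII. Classing the named products on the form as extended half-life is also an assumption.

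**The plan's own figure.** The protocol gives no half-life, dose or recovery, so the 5 days cannot be reproduced. They equal five half-lives only at a half-life of 120/5 = 24 h.

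**Step 1: share of peak left at the minimum interval.** Share = 2^(-t/half-life), independent of dose and recovery. **Step 2: residual** = dose × recovery × share.

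| Product type | Share left | Peak rise (IU/ml) | Residual (IU/ml) |
|---|---|---|---|
| Extended FIX, 120 h | 18.95% (50 h) to 43.53% (100 h) | 0.20-0.65 | 0.038-0.283 |
| Standard FIX, 120 h | 0.98% (18 h) to 3.13% (24 h) | 0.20-0.65 | 0.002-0.020 |
| Extended FVIII, 72 h | 3.59% (15 h) to 7.23% (19 h) | 0.50-1.00 | 0.018-0.072 |
| Standard FVIII, 72 h | 0.20% (8 h) to 2.83% (14 h) | 0.50-1.00 | 0.001-0.028 |

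At 120 h, extended FIX has passed only 120/100 = 1.2 to 120/50 = 2.4 half-lives. The eight combinations of extreme dose, recovery and half-life give 0.0379, 0.0871, 0.0616, 0.1415, 0.0758, 0.1741, 0.1232 and 0.2829. All exceed 0.01 and seven exceed 0.05. These figures are for a sample taken exactly at the minimum; a later one holds less. Only the last dose is counted.

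**Step 3: check against the dosing intervals on the form.** Suppose a regimen still leaves 0.01 IU/ml at the end of its interval, from an assumed peak of 0.5-1.0 IU/ml. A 1-week interval then implies a half-life of 29.8-25.3 h and 0.031-0.037 IU/ml at day 5. A 2-week interval implies 59.5-50.6 h and 0.124-0.193 IU/ml.

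**Step 4: the 6.4.3 ratio.** Take one-stage 0.10 and chromogenic 0.05 (ratio 0.50), with the residual read equally by both assays (assumption).
- Lowest residual at 120 h: (0.05 + 0.0379)/(0.10 + 0.0379) = 0.64. The discrepancy is hidden.
- On-demand patient whose dosing stops by the end of the bleed, so 168 h: residual 0.20 × 2^(-168/50) = 0.0195; ratio (0.05 + 0.0195)/(0.10 + 0.0195) = 0.58. It is still detected.
- Highest residual at 168 h: 0.65 × 2^(-168/100) = 0.203; ratio 0.253/0.303 = 0.83. Hidden.
- With 0.20 and 0.10 instead, the lowest 120 h residual gives 0.1379/0.2379 = 0.58. A residual of 0.05 is needed to reach 0.60.

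**Step 5: time for five half-lives.** Extended FIX: 250-500 h, or 10.4-20.8 days. At that point 1/32 = 3.1% of the peak remains: 0.20/32 = 0.006 to 0.65/32 = 0.020 IU/ml for FIX, and 0.50/32 = 0.016 to 1.00/32 = 0.031 for FVIII.

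**The case against.** The strongest reply is that flags and sensitivity analyses belong in a statistical analysis plan, which is not shown, and that the protocol already collects every input needed. That holds for the analysis rules. It does not remove the fault in the protocol itself: an interval that ignores the product is described as the wash-out for baseline levels, and no later plan can change when a stored sample was drawn.

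A second reply is the 7-day post-bleed rule. It stands for on-demand patients and weakens the effect in 6.4.3, as Step 4 shows. It gives no protection to patients on prophylaxis.

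A third is that all sizes rest on outside figures and that extended half-life products appear in 1.3.4 among novel options. This also stands: the form shows that such products could be recorded, not that they were common.

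A reader might infer more than the documents support:
- **That patients would be put in the wrong severity class.** Section 4.1 enrols patients by registered severity, and 5.1.3 takes baseline levels from the chart. The 0.01 and 0.05 limits serve here only as a scale.
- **That 6.4.3 fails as a whole.** Only mild or moderate haemophilia B patients recently given such a product are touched.
- **That the 3-day FVIII rule is equally at fault.** The extended and standard FVIII residuals overlap.
- **That the half-life remark in 7.4 is wrong.** It concerns bleeding risk, not baseline measurement, and needs no correction.

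**Conclusion.** The point holds in a limited form. For extended half-life FIX, a sample that meets the 5-day rule is not a baseline sample: 19-44% of the peak remains at assumed half-lives of 50-100 h, and this share does not depend on the dose or recovery assumed. The residual of 0.04-0.28 IU/ml does depend on them. The main exposure is haemophilia B patients on prophylaxis with such a product, in the FIX activity and NHA measurements and in CAT where such patients are among the 75. In 6.4.3 the effect can hide a discrepancy, but not in every case. The number of patients is not given and may be small. The change is worth making because it is cheap; confidence is medium because every half-life, dose and recovery is an assumption.

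**What to change.** State in 5.1.2, and where 7.4 refers to baseline levels, that the 3-day and 5-day intervals are a wash-out for standard half-life products only. Do not lengthen the wash-out: 10-21 days without extended FIX would be a burden and a bleeding risk that the study does not need.

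Use the recorded product, dose, weight and time of last infusion to flag samples taken fewer than five product-specific half-lives after infusion. Do not call flagged FIX activity values baseline, and leave them out of the 6.4.3 discrepancy endpoint. For NHA and CAT, report results with and without flagged samples, and give the number and treatment of flagged patients.

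The cost is two sentences, a short list of product half-lives (not in the protocol) and one derived variable, with no extra blood or visits. There are two drawbacks. Patients on weekly extended half-life FIX will nearly all be flagged, since 7 days is shorter than 10.4, so the unflagged analysis under-represents them; this is why both NHA and CAT analyses are kept. And about 3% of the peak remains at the threshold, so the flag removes large residuals only.
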